Identify the Epidural Space with EpiFaithTM Syringe in Air and Saline based Procedures

Short Title:	EpiFaith TM Syringe for Epidural Space Detection
Indication:	Epidural space localization
Protocol Number:	EPS01
Version/Date:	3.0/ March 15, 2019
Study Site:	Taipei Veterans General Hospital
Sponsor:	Flat Medical Co., Ltd.

This protocol is the confidential information of Flat Medical Co., Ltd. and is intended solely for the guidance of the clinical investigation. This protocol may not be disclosed to parties not associated with the clinical investigation or used for any purpose without the prior written consent of Flat Medical Co., Ltd.

Study Title:

Identify the Epidural Space with EpiFaithTM Syringe in Air and Saline based Procedures

Objective:

Clinical Study Protocol

I have read the protocol and agree to conduct this clinical study in accordance with all stipulations of the protocol, with applicable law and regulations and in accordance with the ethical principles outlined in the Declaration of Helsinki.

Principal Investigator:

[name]., Ph. D. Taipei Veterans General Hospital

Date

Study Title:

Identify the Epidural Space with EpiFaithTM Syringe in Air and Saline based Procedures

Objective:

Clinical Study Protocol

I have read the protocol and agree to conduct this clinical study in accordance with all stipulations of the protocol, with applicable law and regulations and in accordance with the ethical principles outlined in the Declaration of Helsinki.

Sponsor:

Flat Medical Co., Ltd.

Date

SYNOPSIS

I. Protocol Title: Identify the Epidural Space with EpiFaith TM Syringe in Air and Saline based Procedures.					
II. Objectives: The objective of the study is to verify the efficacies of both air and saline based procedure of EpiFaith syringe for assisting the needle localization of the epidural space.					
 III. Test device: 1. Name: EpiFaith syringe 2. Manufacturer: Flat Medical Co., Ltd. 3. Method of use: EpiFaith Syringe can provide a visual signal to assist anesthesiologists to localize the epidural space. 4. Device category: Class II 					
IV. Study design:					
1. Controlled: Same device					
other:					
2. Blinding					
□ Double blind □ Double dummy □ Other					
3. Randomized: Yes No					
4. Parallel Cross-over Other					
5. Duration of treatment: 30 minutes					
6. Titration:					
7. Multi-national Multi-center (Taiwan) Single center					
 V. Endpoints: 1. Primary Endpoint(s): Success of epidural localization 2. Secondary Endpoints Time to identify the epidural space Duration of the epidural space localization procedure Number of attempts Number of the occurrence of false positive 					
• The distance from the skin to the epidural space					
• Number of change insertion segment					

VI. Selection criteria:

• Main Inclusion Criteria

- 1. 20 years and older
- 2. Surgery requiring epidural anesthesia or analgesia
- 3. ASA Physical Status 1 to 3

• Exclusion Criteria

- 1. Bleeding and clotting disorders
 - Platelet count $< 100,000 / \text{mm}^3$
 - International normalized ratio (INR) > 1.5
- 2. History of peripheral neuropathy
- 3. Neuromuscular or neuropsychiatric disease
- 4. Marked spinal deformities or a history of spinal instrumentation
- 5. Systemic infection
- 6. Skin infection at the injection site
- 7. Significant heart failure, e.g. New York Heart Association (NYHA) Functional Classification 3 or 4

VII. Study procedures:

This is a single blind, randomized study. Subjects who will receive a surgery requiring epidural anesthesia or analgesia and meet all of the study criteria will be enrolled in the study. All subjects must sign an informed consent and receive a copy of the signed and dated informed consent form prior to participation in the trial.

The study consists of 2 study visits: Visit 1 (Screening Visit) and Visit 2 (Operative Visit). After screening, eligible subject will be randomly assigned to one of the following groups: Group A: detection by EpiFaith syringe with air; Group S: detection by EpiFaith syringe with saline with a 1:1 ratio. In Visit 2, the following variables will be recorded and rated during the process of epidural space localization: Success of epidural localization, time to identify the epidural space, duration of the epidural space localization procedure, number of attempts, Number of the occurrence of false positive, the distance from the skin to the epidural space, and number of change insertion segment. Adverse events and concomitant treatments will be also recorded.

VIII. Concomitant therapy:

1. Prohibited therapy:

The following medications are prohibited within 5 days prior to epidural localization:

- Anti-coagulants (e.g., Warfarin, Heparin, Plavix)
- Antiplatelet
- 2. All concomitant therapies related to epidural localization should be recorded, including AE treatment.

IX. Statistics:		
1. Primary hypothesis:	Superiority	Non-inferiority
	Equivalence	Other

2. Sample size:

Considering the recommendation given by Lancaster, Dodd &Williamson. A total of 60 subjects (30 subjects per group) will be required in this study to obtain parameters such as ratio, mean and standard deviation which will be used in a sample size calculation for the full-scale trial, and to estimate the rate of participants who drop out of the trial.

- **3.** Efficacy population: ■ITT □PP □Other Safety population: □ITT □PP ■Other
- **4.** Statistical method(s) for efficacy/safety evaluations:

Statistical analyses will be reported using summary tables, graphs, and data listings. Analysis are performed with SPSS, Version 20.0 (IBM Corporation, Armonk, NY, USA). The analysis population will be summarized by A and S groups. For categorical variables, frequencies and percentages will be summarized; continuous data will be shown as descriptive statistics. The variables within a normal distribution will be compared using Student's t-tests, and those without a normal distribution will be compared using the Mann-Whitney U test. The number of patients will be compared between the groups using the Fisher's exact test. All information will be summarized and presented in statistical analysis tables. As for data of efficacy and safety variables, no imputation method is applied.

Incidence of the adverse events will be summarized. In the case of CTCAE grade summaries, the most severe event will be presented in summary tables in the case of multiple occurrences per patient. The frequency and the percentage of each category will be presented. All safety parameters, including adverse events, adverse device effect, serious adverse event, serious adverse device effects and unanticipated adverse device effect will be listed by A and S groups. The Medical Dictionary for Regulatory Activities (MedDRA) adverse event dictionary will be used to map verbatim adverse events to preferred terms and system organ class. Fisher's exact test will be applied for comparing the incidences of adverse events between treatment groups.

5. Planned interim analysis: Yes No

X. Schedule of Assessments

Procedures	Screening ⁽³⁾	Operative period	
	Visit 1	Visit 2	
Informed Consent	Х		
Inclusion/Exclusion Criteria ⁽¹⁾	Х	Х	
Medical History	Х		
Demography	Х		
Physical Examination	Х		
Randomization		Х	
Epidural Space Localization Planning		Х	
Epidural Space Localization with Study Test Device		Х	

1. INTRODUCTION

Locating the epidural space is an indispensable part of obstetrical analgesia, surgical anesthesia, postoperative analgesia, and chronic pain control.

The traditional method of locating the position of the needle tip is loss of resistance technique (i.e., the

"LOR"), which is based on detecting the pressure drop occurring at the moment the needle tip reaching the epidural space. Because the pressure of the epidural space is lower than the cavities of others tissue, a free injection of air or liquid from the syringe can be induced, resulting in a sudden loss of resistance of the plunger. Thus, the anesthesiologist can detect the pressure drop by feeling the resistance of pushing the plunger of the attached syringe.

The epidural space is a very thin area near the spinal cord. The advance of needle must be stopped right after the needle tip reaches the epidural space to prevent accidental dural puncture, which may lead to cerebrospinal fluid leakage followed by intractable headache and injuries of the spinal nerves. However, the current incidence rates of accidental dural punctures are 0.19-3.6%¹.

Using the LOR hand feeling to locate epidural space relies on manual skill of the operator and the considerable experiences. Choosing air or saline for LOR technique depends on personal experiences of the operator. The variety of LOR techniques has increased the difficulty of learning².

Some objective and confirmatory devices based on LOR technique are developed, such as Episure and Epidrum, and have been discuss under clinical trial³⁻⁵. The results show a lower failure rate and a shorter time needed to identify the epidural space. However, the restriction of the media and the actuating pressure selection will deprive the anesthesiologists' habit.

The EpiFaith syringe is an improved LOR device with the ability to warn and help physicians to achieve the safe insertion is required. EpiFaith syringe provides objective, and quantitative pressure information as well as a visual signal which is triggered at the moment the needle tip enters the epidural space. Hence, the anesthesiologist can get a clear endpoint for the advancing of the needle easily. The advantages of EpiFaith syringe including that the anesthesiologist can control the epidural needle with both hands and achieve the real- time pressure detection.

The trial quantity of EpiFaith syringe were finished, as well as the biocompatibility testing to ISO 10993, the connector testing to ISO80369-7, epidural simulated testing on ex-vivo and in-vivo porcine spine were performed. Results of testing demonstrate that the EpiFaith syringe meets its performance specifications and is safe and effective for its intended use.

The aim of this study is to evaluate using the EpiFaith syringe with two different sensing medians for epidural localization. The hypothesis of the study is that EpiFaith syringe can detect LOR of epidural space effectively with its achievable pressure. It is beneficial to both junior and senior physicians by transforming the process into a safe and convenient procedure.

2. OBJECTIVE

The objective of the study is to verify the efficacies of both air and saline based procedure of EpiFaith syringe for assisting the needle localization of the epidural space.

3. STUDY DESIGN

3.1. Overall Study Design

This is a single blind, randomized study. Subjects who will receive a surgery requiring combined spinal -epidural technique and meet all of the study criteria will be enrolled in the study. All subjects must sign an informed consent and receive a copy of the signed and dated informed consent form prior to participation in the trial.

The study consists of 2 study visits: Visit 1 (Screening Visit) and Visit 2 (Operative Visit). After screening, eligible subject will be randomly assigned to one of the following groups: Group A: detection by EpiFaith syringe with air, or Group S: detection by EpiFaith syringe with saline with a 1:1 ratio. In Visit 2, the following variables will be recorded and rated during the process of epidural space localization: Success of epidural localization, time to identify the epidural space, duration of the epidural space localization procedure, number of attempts, Number of the occurrence of false positive, the distance from the skin to the epidural space, and number of change insertion segment. Adverse events and concomitant treatments will be also recorded.

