3.2.2. Inclusion criteria

Subjects meeting all of the following criteria will be considered for enrollment into the study:

1. 20 years and older

- 2. Surgery requiring epidural anesthesia or analgesia
- 3. ASA Physical Status 1 to 3

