5.1.2. Eligibility and inform consent

Subjects will be screened prior to the start of the study treatment. All assessments will be performed after the subjects have signed and dated the inform consent form.

The investigator or a designee will explain the nature of the study to subjects who will undergo surgery requiring epidural space localization. The subject will be given an informed consent form to be read carefully before agreeing to take part in the study and before the study-specific procedures take place. The informed consent form should be reviewed, signed, and dated by the subject and counter-signed by the investigator. A copy of the statement will be given to the subject, and the original should be maintained by the investigator in the site master file. After informed consent being obtained, designed procedures and assessments will be initiated to determine eligibility.

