5.2.5. Epidural space localization procedure

Subjects will undergo the surgical procedure using epidural space localization in a medical center with appropriate facilities and by appropriately trained personnel.

Epidural space localization planning will be completed before the epidural space localization. The plan should be recorded, and the records should include surgery name, insertion segment.

During epidural space localization, the subject are in the lateral position. After cleaning and draping the area, a local anesthetic is infiltrated at the insertion site of epidural needle.

Anesthesiologist inserted the epidural needle at least 3cm to pass the subcutaneous tissue. Pull out the stylet and attach the filled EpiFaith syringe. In Group A, the EpiFaith syringe is filled with air; in Group S, the EpiFaith syringe is filled with saline. Then, push the plunger to create a continuous pressure inside the syringe. When the needle arrived the epidural space, due to LOR occurred, the piston of EpiFaith syringe will move forward. The clear visual signal can warn the operator the localization of needle tip. After the detection of LOR, the catheter will be inserted though the needle. When the catheter can protrude from the needle tip at least 3cm, which can be identified by the graduations on its surface, the test dose (2 ml of 2% lidocaine) of anesthetic will be injected. After injection for 15min, the cold sensation test will be performed, by comparing the perception of cold of alcohol sponges between the blocked dermatomes and face. The tests will be bilaterally, and repeated 3 times in 3 difference dermatomes on each side.

If the visual signal occurs but the catheter cannot be inserted to protrude the needle tip at least 3 cm, which means the false positive occurs.

If the catheter is inserted successfully and the test dose of anesthetic is injected, but the result of cold sensation test shows the perception of cold exists in the blocked dermatomes by cold sensation test and exclude the reason is due to dose and drug failure, which also means the false positive occurs.

If the inadvertent dural puncture occurs, the success of epidural localization will be recorded failed. There is no necessary to record all secondary outcome. The physician can use the traditional LOR syringe or other method to compete the procedure.

The process of epidural space localization will be simultaneously recorded by video.

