7. STUDY ENDPOINTS

7.1. Primary Endpoint

• Success of epidural localization

(defined as the catheter can be inserted into epidural space successfully, no cold perception in the blocked dermatomes after the injection of anesthetic by cold sensation test, and no occurrence of inadvertent dural puncture.)

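### Section 3.1 enrols combined spinal-epidural surgery while the synopsis, 3.2.2 and 5.2.5 describe epidural procedures only; if an intrathecal drug is already acting at the cold test, that part of the primary endpoint no longer shows that the catheter is epidural.

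*Combined protocol and SAP*

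**What the plan says.** The population is worded in more than one way in the current text of the combined protocol and SAP.

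- Section 3.1 enrols subjects who will have "surgery requiring combined spinal -epidural technique".
- Synopsis VII, otherwise the same sentence: "Subjects who will receive a surgery requiring epidural anesthesia or analgesia and meet all of the study criteria will be enrolled in the study".
- Section 3.2.2, criterion 2 (and Synopsis VI): "Surgery requiring epidural anesthesia or analgesia".
- Section 5.1.2, on whom to approach for consent: "subjects who will undergo surgery requiring epidural space localization".

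No exclusion criterion in 3.2.3 mentions a combined spinal-epidural technique.

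The primary endpoint (7.1, repeated in 5.2.5.1) has three components: successful catheter insertion, absence of inadvertent dural puncture, and "no cold perception in the blocked dermatomes after the injection of anesthetic by cold sensation test". The route of that injection is not named in the definition. Section 5.2.5 supplies the sequence: loss of resistance, catheter through the needle to at least 3 cm past the tip, a test dose, and then "After injection for 15min, the cold sensation test will be performed". It describes no spinal needle and no intrathecal drug. The false-positive endpoint (5.2.5.1 and 7.2) uses the same cold test.

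**The concern.** Subjects having a combined spinal-epidural technique can enter under either wording. Under 3.1 they are the whole study. Under 3.2.2 they can reasonably qualify, since their procedure has an epidural component and nothing excludes them.

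The cold test is meant to show that drug given through the catheter has reached the epidural space. An intrathecal drug can abolish cold perception by itself. A reading taken while such a drug is acting would be passed whether or not the catheter is epidural. Section 5.2.5 discounts a failed cold test that is due to dose or drug failure, but has no counterpart for a test passed because of a different drug.

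At stake are the success rate, the false-positive count, and their later use: section 8.1 says the 60 subjects are to supply parameters for the sample size of a full-scale trial.

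**Working it through.** **Text comparison.** Section 3.1 and Synopsis VII differ only in the phrase naming the procedure. The synopsis agrees with 3.2.2, and 5.2.5 fits the synopsis better than 3.1. The difference lies between current passages.

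**The plan's own figure.** Section 8.1 gives 30 per group, and 2 × 30 = 60. It states no success rates, alpha or power, so nothing further can be reproduced.

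**Size of the possible effect.** All rates here are assumptions; the documents give none.

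- q = true cold-test failure rate
- f = share of subjects with an intrathecal drug acting at the reading, each assumed to pass the test and to be no more or less likely to have a misplaced catheter
- r = failure rate on the other two components

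Observed success = (1 − r) × [1 − q(1 − f)], so the overstatement is (1 − r) × q × f. With r = 0:

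| q | f = 0 | f = 50% | f = 100% |
|---|---|---|---|
| 5% | 0 points | 2.5 | 5 |
| 10% | 0 | 5 | 10 |
| 20% | 0 | 10 | 20 |
| 30% | 0 | 15 | 30 |

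With r = 5% and q = 10%, full masking adds 0.95 × 10 = 9.5 points (85.5% to 95.0%).

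In one arm of 30 with q = 10% and r = 0, expected cold-test failures are 30 × 0.10 × (1 − f): 3, 1.5 and 0 at f = 0, 50% and 100%. At the extreme, 27/30 (90%, exact 95% CI 73% to 98%) would be reported as 30/30 (100%, 88% to 100%). The false-positive count falls by the same failures.

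**Comparison of arms.** The difference due to the cold test is (1 − r)(1 − f)(q_A − q_S), so it shrinks by the factor 1 − f. Section 8.4.1 specifies Fisher's exact test. Its exact power, with 30 per arm, two-sided 0.05 (assumed) and r = 0, is:

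| q_A vs q_S | f = 0 | f = 50% | f = 100% |
|---|---|---|---|
| 20% vs 5% | 0.24 | 0.04 | 0 |
| 30% vs 5% | 0.63 | 0.16 | 0 |
| 40% vs 5% | 0.89 | 0.37 | 0 |

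The trial is a pilot and was not sized for power; the table only shows how masking would remove the endpoint's ability to separate the arms.

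**The case against.** The strongest reply is that masking is not in the documented procedure. Section 5.2.5 sets out a plain epidural sequence, and read with it the injection in the endpoint definition is the epidural test dose. Masking needs an injection that the protocol does not describe, at a time it does not give. This stands, and it makes the second half of the point conditional. A reader might infer that success will in fact be inflated; the documents do not support that. If any intrathecal drug came after the cold reading, the endpoint would be unaffected.

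Three further limits also stand.

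- A reader might take the cold test to be the sole check on the catheter. Section 7.1 separately requires catheter insertion and no inadvertent dural puncture, so masking cannot make the whole endpoint succeed. Insertion is judged by graduations on the catheter, however, which leaves the cold test as the main functional check of position.
- A reader might call the population undefined. The eligibility lists agree with each other, and 3.1 itself requires subjects to meet the study criteria. The text is inconsistent, with one narrative sentence as the outlier.
- Under 1:1 randomization, masking would be expected in both arms, so it dilutes a difference and gives no systematic advantage to air or saline.

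Some information on affected subjects may also exist already: section 3.6 records concomitant therapies related to localization, and 5.2.5 records surgery name and insertion segment and requires video. None of these requires the technique, or the timing of an intrathecal drug relative to the cold reading, to be recorded.

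**Conclusion.** The inconsistency between 3.1 and the synopsis, 3.2.2 and 5.2.5 is certain and needs correcting. The effect on the endpoint is a possibility that the protocol leaves open: it requires both that combined spinal-epidural subjects are enrolled and that an intrathecal drug is acting when cold is tested. In that case success is overstated by up to q × f (0 to 10 points at an assumed q of 10%), false positives are undercounted, and any air-saline difference in the cold-test component shrinks by the factor 1 − f. The values of f, q and r are assumptions, and the 10-point figure is the extreme at which every subject is masked. The point is worth acting on before enrolment because the pilot's rates feed the next trial's sample size, and the technique may be hard to recover afterwards if it was not recorded.

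**What to change.** State one population, in the same words, in 3.1, the synopsis, 3.2.2 and 5.2.5, and align 5.1.2. Which population is intended is for the sponsor and the investigator to decide.

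If combined spinal-epidural subjects remain eligible:

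- In 5.2.5.1 and 7.1, say that the injection referred to is the epidural test dose.
- Record on the CRF the technique used and whether any intrathecal drug preceded the cold reading.
- Where one did, treat the cold-test component as not evaluable, neither success nor failure. This fits the no-imputation rule in 8.4. Failure on catheter insertion or inadvertent dural puncture remains a failure.
- Report success and false positives with and without these subjects. For the second analysis, leave them out whatever their other components show, so that failures alone are not retained.

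These are rules for scoring and reporting. They should not prescribe when any drug is given.

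The cost is some protocol wording, two CRF items and one sensitivity analysis. The real downside is fewer evaluable cold readings: at f = 50%, 30 × 0.5 = 15 per arm, and the exact lower 95% limit for an all-success arm falls from 0.025^(1/30) = 88% to 0.025^(1/15) = 78%. If 3.1 is the intended population the loss could be larger still, which is a reason to settle the population first.
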